5.1.2 Stopping Rules

For dose escalation (group)

At each planned safety review, safety data will be reviewed and a GO/NO GO decision made accordingly for enrolment of further subjects and administration of subsequent doses.

Enrolment or administration at the given dose level will be temporarily halted and only continued after DSMB approval and approval by the competent authority following the occurrence of:

- Any related SAE in the opinion of the principal investigator (PI), the DSMB and/or the iSRC.
- Related severe AEs of the same kind in $\geq 20\%$ of the subjects in one group with the following exceptions:
 - Transient grade 3 chills, fatigue, headache, fever, myalgia or arthralgia resolving within 24 hours to grade ≤ 2 .
 - Transient grade 3 local AEs reducing to grade ≤ 2 within 48 hours.

Based on the review of the data, the DSMB will decide about temporary or permanent stopping of dosing in the given and eventually also lower dose groups (pertaining to the 2nd dose administration). After a temporary halt further measures for safety monitoring (i.e. additional safety visits including safety blood sampling at additional time points) may also be introduced based on DSMB recommendation.

For further CV7202 dose administration (subject)

Subjects must not receive a second dose of CV7202 in the event of:

- Occurrence of an allergic/anaphylactic reaction after the first dose.
- Any related SAE in the opinion of the PI, the DSMB and/or the iSRC.
- Any related severe (grade 3) AEs with the following exceptions:
 - Transient grade 3 chills, fatigue, headache, fever, myalgia or arthralgia resolving within 24 hours to grade ≤ 2 .
 - Transient grade 3 local reactions resolving to grade ≤ 2 within 48 hours.

If these reactions occur, the subject must not receive additional vaccinations but is encouraged to continue in trial participation for safety reasons, including collection of safety blood samples. Immunogenicity assessments may be performed at the investigator's discretion and if the subject agrees.

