6.4 Interim Analysis and Data Monitoring

One or more interim analyses (IAs) may be performed for this trial. The data will be cleaned for all subjects. The analyses will be based on a data snapshot. Analyses will be performed on the safety set or subsets of it based on the availability of data. No decision-making is planned for the IAs and no adjustments for the trial are planned based on the results.

It is not planned to discuss any difference between the IAs and the final analysis in the clinical trial report.

A first interim analysis was performed after 16 subjects had been vaccinated (10 subjects in the CV7202 5 µg group and 6 subjects in the Rabipur group) and observed until Visit 8. The first interim analysis focused on safety aspects only. It was planned in a standalone interim analysis plan, which was finalized on 6 February 2019.

The second interim analysis was performed after 53 subjects had been vaccinated (16 subjects in the CV7202 1 µg group, 16 subjects in the CV7202 2 µg group, 10 subjects in the CV7202 5 µg group and 11 subjects in the Rabipur group) and observed until Visit 12 (Day 57). The second interim analysis focused on safety and immunogenicity. The analysis was primarily based on the interim analysis plan as of 06 February 2019 and subsequent change requests for tables.

For details of data monitoring please refer to section 4.

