7. NOTATION OF VACCINATION GROUPS AND VISITS

Notation of vaccination groups

The following notation of **vaccination groups** will be used throughout the report:

Full notation (as used in the trial protocol)	Notation as used throughout all tables, listings and figures
Group 3 
 • Group 3 without Group 3a • Group 3a 	CV7202 1 µg 
 • CV7202 1x1 µg • CV7202 2x1 µg
Group 4 
 • Group 4 without Group 4a • Group 4a 	CV7202 2 µg 
 • CV7202 1x2 µg • CV7202 2x2 µg
Group 2	CV7202 5 µg
Group 1	Rabipur

The administration of a second dose to every 8 of the 16 subjects in groups 3 and 4 was done in a sequential manner at the sites. Therefore this analysis does not differentiate between planned and actual vaccination group and done regimen and all analyses will be based on the actually received vaccination group and dose regimen.

Visit terminology

Visit	Notation as used throughout all tables, listings and figures¹
Visit 1 (Pre-screening Visit, Days -90 to -1)	V1 (Pre-screening)
Visit 2 (Screening Visit, Days -30 to -1)	V2 (Screening)
Visit 3 (Vaccination Dose 1 CV7202 or Rabipur, Day 1)	V3 (Day 1)
Visit 4 (Day 2 or 3*)	V4 (Day 2/3)
Phone call (Day 3)	Phone call 1 (Day 3)
Visit 5 (Vaccination Dose 2 Rabipur, Day 8)	V5 (Day 8)
Visit 6 (Day 10)	V6 (Day 10)
Visit 7 (Day 15)	V7 (Day 15)
Visit 8 (Vaccination Dose 2 CV7202 or Dose 3 Rabipur, Day 29)	V8 (Day 29)
Visit 9 (Day 30 or 31**)	V9 (Day 30/31)
Phone call (Day 31)	Phone call 2 (Day 31)
Visit 10 (Day 36)	V10 (Day 36)
Visit 11 (Day 43)	V11 (Day 43)
Visit 12 (Day 57)	V12 (Day 57)
Visit 13 (Day 91)	V13 (Day 91)
Visit 14 (Month 6: Day 181 [1-dose regimens]/ Day 209 [2-dose regimens and Group 1 {Rabipur}])	V14 (Month 6)
Optional Visit 14A***	V14A (M6+3)
Visit 15 (Month 12: Day 365 [1-dose regimens]/ Day 393 [2-dose regimens and Group 1 {Rabipur}])	V15 (Month 12)
Optional Visit 15A***	V15A (M12+3)
Visit 16 (Month 18: Day 547)	V16 (Month 18)
Optional Visit 16A***	V16A (M18+3)
Visit 17 (Trial End) (Month 24: Day 729)	V17 (Trial End/Month 24)
Optional Visit 17A***	V17A (M24+3)

* It should be noted that for subjects enrolled in the trial before Protocol Amendment 1 became effective, Visit 4 occurred on Day 3 as planned in the original protocol.

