Arthralgia	2	Moderate, some interference with normal activity
	3	Significant, prevents normal activity
	0	Absent
Nausea/ Vomiting	1	Mild, no interference with normal activity
	2	Moderate, some interference with normal activity
	3	Significant, prevents normal activity
Diarrhea	0	Absent
	1	2 or 3 loose stools or <400 g/24 hours
	2	4 or 5 stools or 400 – 800 g/24 hours
	3	6 or more watery stools or >800 g/24 hours or requires outpatient i.v. hydration

*United States Food and Drug Administration toxicity grading scale; i.v. = intravenous.

Solicited AEs are also documented as AEs on the respective eCRF pages by the investigator, if they are serious and/or are ongoing on Day 8.

For every solicited AE, the maximum over all grades documented in the diary on the day of vaccination and the 7 subsequent days will be defined as grade (intensity) of this solicited AE.

Frequencies and percentages of local and systemic solicited AEs reported on the day of vaccination and the 7 subsequent days will be displayed by vaccination group, by subject overall and vaccination dose (number).

An overall summary table will display frequencies and percentages by grade (intensity) including any grade of:

- Any solicited AEs
- Local solicited AEs

- Systemic solicited AEs
- Related systemic solicited AEs
- Any solicited AEs ongoing on Day 8

Frequencies and percentages by grade (intensity), including any grade, will also be displayed for the individual terms of solicited AEs. Gradings of zero (AE is absent) will not contribute to the numbers tabulated.

The duration in days of a solicited AE will be represented by the number of days with diary entries of Grade ≥ 1 (out of Days 1-8) reported by a subject per solicited AE term and diary (corresponding to vaccination dose). Thus, the duration in days can range from 1 to 8 per prespecified solicited event term and vaccination dose administered.

The duration of Grade 3 solicited AEs will be derived by counting only days with Grade 3 entries.

For subjects without a specified event term, no duration of this event will be calculated, ie, no zero durations are possible.

The number of days of solicited AEs, as well as the number of days of solicited Grade 3 AEs will be tabulated with basic statistics by vaccination group and vaccination dose (number) for any solicited AE, any local solicited AE, any systemic solicited AE, any related systemic solicited AE, and the individual terms of solicited AEs.

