14.2.3.4 Cytokine Assessment by Dosage/Vaccine and Treatment Group, Full Analysis Set

	CV7202 1x1 µg (N = xx)	CV7202 2x1 µg (N = xx)	CV7202 1x2 µg (N = xx)	CV7202 2x2 µg (N = xx)
Parameter (unit)	Baseline			
n	xx	xx	xx	xx
Mean (SD)	xx.x (xx.xx)	xx.x (xx.xx)	xx.x (xx.xx)	xx.x (xx.xx)
Median	xx.x	xx.x	xx.x	xx.x
Min, Max	xx, xx	xx, xx	xx, xx	xx, xx
	Actual result (Visit xx)			
n	xx	xx	xx	xx
Mean (SD)	xx.x (xx.xx)	xx.x (xx.xx)	xx.x (xx.xx)	xx.x (xx.xx)
Median	xx.x	xx.x	xx.x	xx.x
Min, Max	xx, xx	xx, xx	xx, xx	xx, xx
	Change from baseline (Visit xx)			
n	xx	xx	xx	xx
Mean (SD)	xx.x (xx.xx)	xx.x (xx.xx)	xx.x (xx.xx)	xx.x (xx.xx)
Median	xx.x	xx.x	xx.x	xx.x
Min, Max	xx, xx	xx, xx	xx, xx	xx, xx

PROGRAM SOURCE: tlf-###, DATA CUT OFF DATE: DDMMYYYY

RUN DATE: DDMMYYYY hh:mm

Programming note:

Display for available parameters with sufficient data and visits with scheduled sampling.

Number of decimals will vary by lab parameter - in general present mean, median to 1 decimal more than individual data, SD to 2 decimals more than individual data. Refer to SAP.

Sponsor
Protocol number

Clinical Study Report
Page x of y

14.3.1.1.1.1 Summary of Solicited Adverse Events Within 7 Days After any Dose, Safety Analysis Set

Category [n (%)]	CV7202	CV7202	CV7202	Rabipur	
	1 µg (N = xx)	2 µg (N = xx)	5 µg (N = xx)	(N = xx)	
Any solicited adverse event	AE (Grade 1,2,3) No AE (Grade 0) Grade 1 (mild) Grade 2 (moderate) Grade 3 (severe) Not assessed	xx (xx.x%) xx (xx.x%) xx (xx.x%) xx (xx.x%) xx (xx.x%) xx (xx.x%)			
Any local solicited adverse event	AE No AE ..	xx (xx.x%) xx (xx.x%) xx (xx.x%)	xx (xx.x%) xx (xx.x%) xx (xx.x%)	xx (xx.x%) xx (xx.x%) xx (xx.x%)	
Any systemic solicited adverse event					
Any related systemic solicited adverse event					
Any solicited adverse event ongoing on day 8					
Any local solicited adverse event ongoing on day 8					
Any systemic solicited adverse event ongoing on day 8					

n = Number of subjects

Subjects are counted once based on highest severity.

Percentages are based on total no. of subjects in each vaccination group.

PROGRAM SOURCE: tlf-###, DATA CUT OFF DATE: DDMMYYYY

RUN DATE: DDMMYYYY hh:mm

Sponsor
Protocol number

Clinical Study Report
Page x of y

14.3.1.1.1.2 Summary of Solicited Adverse Events Within 7 Days Post Dose 1, Safety Analysis Set

Category [n (%)]	CV7202 1 µg (N = xx)	CV7202 2 µg (N = xx)	CV7202 5 µg (N = xx)	Rabipur (N = xx)	

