Any solicited adverse event	AE (Grade 1,2,3) No AE (Grade 0) Grade 1 (mild) Grade 2 (moderate) Grade 3 (severe) Not assessed	xx (xx.x%) xx (xx.x%) xx (xx.x%) xx (xx.x%) xx (xx.x%) xx (xx.x%)			
Any local solicited adverse event	AE (Grade 1,2,3) No AE (Grade 0) ..	xx (xx.x%) xx (xx.x%) xx (xx.x%)	xx (xx.x%) xx (xx.x%) xx (xx.x%)	xx (xx.x%) xx (xx.x%) xx (xx.x%)	
Any systemic solicited adverse event					
Any related systemic solicited adverse event					
Any solicited adverse event ongoing on day 8					
Any local solicited adverse event ongoing on day 8					
Any systemic solicited adverse event ongoing on day 8					

n = Number of subjects

Subjects are counted once based on highest severity.

Percentages are based on total no. of subjects in each vaccination group.

PROGRAM SOURCE: tlf-###, DATA CUT OFF DATE: DDMMYYYY

RUN DATE: DDMMYYYY hh:mm

Sponsor
Protocol number

Clinical Study Report
Page x of y

14.3.1.1.1.3 Summary of Solicited Adverse Events Within 7 Days Post Dose 2, Safety Analysis Set

Category [n (%)]	CV7202 2x1 µg (N = xx)	CV7202 2x2 µg (N = xx)	Rabipur (N = xx)	
Any solicited adverse event	AE (Grade 1,2,3) No AE (Grade 0) Grade 1 (mild) Grade 2 (moderate) Grade 3 (severe) Not assessed	xx (xx.x%) xx (xx.x%) xx (xx.x%) xx (xx.x%) xx (xx.x%) xx (xx.x%)	xx (xx.x%) xx (xx.x%) xx (xx.x%) xx (xx.x%) xx (xx.x%) xx (xx.x%)	xx (xx.x%) xx (xx.x%) xx (xx.x%) xx (xx.x%) xx (xx.x%) xx (xx.x%)
Any local solicited adverse event	AE (Grade 1,2,3) No AE (Grade 0) ..	xx (xx.x%) xx (xx.x%) xx (xx.x%)	xx (xx.x%) xx (xx.x%) xx (xx.x%)	xx (xx.x%) xx (xx.x%) xx (xx.x%)
Any systemic solicited adverse event				
Any related systemic solicited adverse event				
Any solicited adverse event ongoing on day 8				
Any local solicited adverse event ongoing on day 8				
Any systemic solicited adverse event ongoing on day 8				

n = Number of subjects

Subjects are counted once based on highest severity.

Percentages are based on total no. of subjects in each vaccination group.

PROGRAM SOURCE: tlf-###, DATA CUT OFF DATE: DDMMYYYY

RUN DATE: DDMMYYYY hh:mm

Sponsor

Clinical Study Report

Protocol number

Page x of y

14.3.1.1.1.4 Summary of Solicited Adverse Events Within 7 Days Post Dose 3, Safety Analysis Set

Rabipur

Category [n (%)]	(N = xx)
------------------	----------

Any solicited adverse event	AE (Grade 1,2,3) xx (xx.x%) No AE (Grade 0) xx (xx.x%) Grade 1 (mild) xx (xx.x%) Grade 2 (moderate) xx (xx.x%) Grade 3 (severe) xx (xx.x%) Not assessed xx (xx.x%)

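### No solicited adverse event table shows Dose 1 in the subjects who had two doses of CV7202; this departs from Protocol 10.3.1 and SAP 12 does not record it

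*SAP*

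**What the plan says.** **Display rule.** SAP 11.2.1 states that frequencies and percentages of solicited events "will be displayed by vaccination group, by subject overall and vaccination dose (number". A subject's grade for an event is "the maximum over all grades documented in the diary" over the day of vaccination and the next 7 days.

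**Shells.** The shell titled "14.3.1.1.1.2 Summary of Solicited Adverse Events Within 7 Days Post Dose 1, Safety Analysis Set" has columns for CV7202 1 µg, 2 µg, 5 µg and Rabipur. The shell titled "14.3.1.1.1.3 Summary of Solicited Adverse Events Within 7 Days Post Dose 2, Safety Analysis Set" has columns for CV7202 2x1 µg, 2x2 µg and Rabipur. The local, systemic, related systemic, duration, daily and onset shells repeat this pattern, directly or through a programming note. The any-dose shells are pooled as well.

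**Numbers.** SAP 6.4 says the second interim analysis was run "after 53 subjects had been vaccinated (16 subjects in the CV7202" 1 µg group, and 16 in the 2 µg group). Protocol Table 8.1 plans 8 re-dosed subjects per level. SAP 7 describes second doses given to 8 of the 16 in each group and adds that "all analyses will be based on the actually received vaccination group and dose regimen".

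**Columns required.** Protocol 10.3.1 wants Groups 3a and 4a shown separately in every table, listing and figure. SAP 6 gives regimen columns only in a selection of tables. SAP 12 records one change, the dropped per-protocol sets.

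**Who may be re-dosed.** Protocol 5.1.2 opens its subject-level rule with "Subjects must not receive a second dose of CV7202 in the event of" and lists an allergic or anaphylactic reaction, a related SAE, and "Any related severe (grade 3) AEs with the following exceptions". The exceptions are grade 3 chills, fatigue, headache, fever, myalgia or arthralgia falling to grade 2 or below within 24 hours, and grade 3 local reactions doing so within 48 hours.

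**The concern.** The synopsis gives the choice of dose and of the number of doses as the trial's purpose. On the safety side, the number of doses turns largely on whether the second injection is tolerated better or worse than the first. The solicited tables are where a reader will look, and they set Dose 1 in 16 subjects against Dose 2 in 8 of them. A difference between the two tables mixes any change from first to second dose with the difference between the 8 and the full 16.

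The 8 need not resemble the 16. Allocation was not randomized, and Protocol 5.1.2 removes some poor Dose 1 reactors from eligibility. CV7202 alone is affected: the 5 µg group had one dose, and the Rabipur column plans the same subjects through all three doses.

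Unsolicited events show a related inconsistency. SAP 11.2.2 promises each AE summary by vaccination group and dose regimen, but shell 14.3.1.2.2 (28 days after Dose 1) has pooled columns only.

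**Working it through.** **1. Denominators.** Protocol Table 8.1 gives 42 CV7202 subjects on Day 1 and 16 on Day 29. These reproduce: 10 + 16 + 16 = 42 and 8 + 8 = 16. So the CV7202 denominators at 1 µg and 2 µg are 16 after Dose 1 and 8 after Dose 2.

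**2. Columns in the solicited shells.**

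| Shell family | Post-Dose 1 columns | Post-Dose 2 columns |
|---|---|---|
| Summary, local, systemic, related systemic (14.3.1.1.1.x) | 1 µg, 2 µg, 5 µg, Rabipur | 2x1 µg, 2x2 µg, Rabipur |
| Number of days (14.3.1.1.2.x) | same pooled columns | same re-dosed columns |
| Daily (14.3.1.1.3.x) | same pooled columns | same re-dosed columns |
| First onset (14.3.1.1.4.x) | same pooled columns | same re-dosed columns |

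None has a 2x1 µg or 2x2 µg column after Dose 1.

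**3. Nobody refused Dose 2, and the 8 unrelated to outcome.** This is chance imbalance, not bias. Assume D of the 16 have an event after Dose 1. The number X among the re-dosed 8 is hypergeometric: P(X = x) = C(D, x) · C(16 − D, 8 − x) / C(16, 8), with C(16, 8) = 12,870. The 8 match the printed rate only when X = D/2.

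| D assumed | Printed Dose 1 rate | P(off by 12.5 points or more) | P(off by 25 points or more) |
|---|---|---|---|
| 4 | 25% | 1 − 5,544/12,870 = 0.569 | 990/12,870 = 0.077 |
| 6 | 37.5% | 1 − 5,040/12,870 = 0.608 | 1,530/12,870 = 0.119 |
| 8 | 50% | 1 − 4,900/12,870 = 0.619 | 1,698/12,870 = 0.132 |

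Since 12.5 points is one subject in 8, the third column is the chance that the 8 differ from an even split by at least one subject.

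**4. Some subjects refused Dose 2.** Let k be the number refused for a grade 3 diary event, e the number re-dosed despite an exempt grade 3 event, and u the number with grade 3 who were neither refused nor re-dosed. The printed Dose 1 Grade 3 rate is (k + e + u)/16; the rate in the re-dosed subjects is e/8. All counts below are assumptions, and the denominator of 8 further assumes that a refused subject's place was filled. Let 1 of 8 (12.5%) have grade 3 after Dose 2.

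| k, e, u | Printed Dose 1 | Re-dosed subjects' own Dose 1 | Printed change | Same-subject change |
|---|---|---|---|---|
| 1, 0, 0 | 6.25% | 0% | +6.25 | +12.5 |
| 2, 0, 0 | 12.5% | 0% | 0 | +12.5 |
| 3, 0, 0 | 18.75% | 0% | −6.25 | +12.5 |
| 1, 1, 0 | 12.5% | 12.5% | 0 | 0 |
| 0, 0, 1 | 6.25% | 0% | +6.25 | +12.5 |

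The first three rows stay below the group halt in Protocol 5.1.2 (0.20 × 16 = 3.2, so 4 subjects with the same kind of event). In the fourth row one exempt event among the re-dosed removes the gap. The fifth gives the same figures as the first with nobody refused. If places were not refilled, k = 1 among the scheduled 8 would leave 7, and one subject would be 1/7 = 14.3 points.

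**The case against.** The case against rests on five arguments.

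- **The screen is narrow.** Most grade 3 solicited events are exempt if they settle in time, and Protocol 5.8.1 expects such reactions typically to resolve within 24 hours. Only nausea/vomiting and diarrhea have no transient exemption. This stands: re-dosed subjects may have had grade 3 events after Dose 1.
- **Nobody is reported as refused.** This also stands. Protocol 7.2 limits replacement of discontinued subjects to a narrow exception, so the assumption that places were refilled is itself uncertain.
- **Sixteen is the better Dose 1 estimate.** True for Dose 1 alone, and the pooled columns should remain the main result. It does not help a reader comparing the doses.
- **No endpoint asks for a within-subject comparison.** Correct, but Protocol 10.3.1 does ask for the columns.
- **Other outputs exist.** Shell 14.3.5.4 shows re-dosed subjects after both doses, but only for local symptoms assessed by the investigator. Listings 16.2.7.2.1 and 16.2.7.2.2 allow a hand count. Shell 14.3.6, listing 16.2.5, listing 16.2.7.1.4 and the discontinued-vaccination rows help to identify who stopped. However, SAP 11.2.1 puts a solicited event on the AE pages only if it is serious or ongoing on Day 8, so a short barring diary event may not appear in those rows. Systemic solicited events have no same-subject table.

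A reader might infer that the tables are biased in favour of Dose 2, or that they will print the wrong direction of change. The documents do not support this. The sign reverses in only one of the assumed cases above, and that case sets every Dose 1 grade 3 event to be a barring one.

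**Conclusion.** The reporting gap is certain: no solicited table shows Dose 1 in the subjects who had both doses. It departs from Protocol 10.3.1 without an entry in SAP 12. For unsolicited events, shell 14.3.1.2.2 also conflicts with the SAP's own text in 11.2.2.

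A distortion in favour of Dose 2 is possible, not shown. It requires that at least one subject was refused Dose 2 under Protocol 5.1.2 and that the event is not balanced by exempt events among the re-dosed. Its size cannot be stated from the documents. The chance figures of 57% to 62% describe how seldom 8 subjects mirror 16 exactly and should not be quoted as bias.

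The trial is descriptive and its subject-level data are preserved, so this is a worthwhile correction to the outputs rather than a threat to the trial.

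**What to change.** 1. Add 2x1 µg and 2x2 µg columns, by regimen received, beside the pooled columns in post-Dose 1 shells 14.3.1.1.1.2, .6, .10 and .14, and in duration shells 14.3.1.1.2.1, .4, .7 and .10. The pooled columns remain the main Dose 1 result.
2. Add the same columns to 14.3.1.2.2, as SAP 11.2.2 already provides.
3. Footnote each post-Dose 2 shell with the number of subjects at that level not given Dose 2 under Protocol 5.1.2, printing 0 if none. Protocol 7.1 already has the reason for stopping CV7202 recorded in the eCRF.
4. Record in SAP 12, as a departure from Protocol 10.3.1, any table where the columns are still omitted, for example the daily and onset shells.
5. Optionally, count re-dosed subjects whose maximum grade after Dose 2 was lower than, equal to or higher than after Dose 1. This needs a new paired derivation and is not essential once the columns exist.

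Items 1 to 4 use data already collected and need small changes to existing programs. The cost is wider tables and columns of 8 in which one subject is 12.5 points. No rule on giving or withholding vaccine changes.
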